10. ADVERSE EVENT REPORTING

Serious adverse events that meet any of the following criteria:

- fatal or life-threatening
- result in significant or persistent disability,
- require or prolong hospitalization,
- neonatal death,

• are important medical events that investigators judge to represent significant hazards or harm to research participants.

Specifically, any AE that meets any of these criteria (maternal death, ICU admission stroke, myocardial infarction, cardiomyopathy, fetal death or neonatal death) will be documented and reported as a SAE.

In addition, any unexpected event/ unanticipated problems which the investigator identifies will be reported.

10.1 Data Safety Monitoring Plan

A DSMP will be in place to ensure the safety of participants by analyzing data and to oversee the validity and integrity of the data.

Any serious adverse event or unanticipated problem will be reported to the Stanford IRB. A Data Safety Monitoring Plan (DSMP) will be established to guide all aspects of the study and oversee participant safety. DSMP participants include the research team. The DSMP will be implemented to monitor safety, to advise on study progress and performance, protocol modification, or whether there should be early termination.

The outcome of reviews will be relayed to the IRB and protocol director.

10.2 Reporting of Adverse Events

In addition, the following maternal or neonatal events are examples of adverse events to be reported:

- Maternal or perinatal allergic reaction
- Angioedema, anaphylaxis or generalized skin rash
- Transfer to Chronic Care facility (neonatal)
- Maternal arrhythmia (especially QT prolongation) or congestive cardiac failure (EF<45%)
- Neonatal arrhythmia (especially QT prolongation)
- Any adverse event leading to discontinuation of study medication or suspected to be due to the medication
- Maternal pulmonary thromboembolism
- Maternal admission to ICU
- Neonatal IVH Grade III or IV
- Prolonged maternal or term neonatal hospitalized

11. QUALITY CONTROL

Quality control and assurance are the responsibility of every member of the MiLI trial.

All clinic personnel are responsible for understanding the protocol procedures.

Research Staff responsibilities:

- Maintaining the integrity of the protocol and regulatory document binder.
- Developing a data entry system that incorporates real-time data quality assurance features, such as range and logic checks
- Monitoring site initiation requirements.
- Monitoring the screening and randomization processes to ensure randomization of eligible participants and appropriate randomization allocation of participants.
- Generating timely web-based reports describing clinic and study performance, including but not limited to: a) recruitment b) visit adherence and visit completeness c) study intervention) data entry e) data completeness f) outcomes documentation
- Monitoring documentation of 100% of potential outcomes

12. STATISTICAL ANALYSIS

12.1 Statistical Considerations

Efficacy Endpoint(s): The primary outcomes include generation of preliminary data comparing obstetric and neonatal outcomes among patients randomized to misoprostol 50 mcg versus mifepristone 200 mg **a**) **obstetric outcomes**: number of uterine contractions– with and without

fetal heart rate decelerations in labor, uterine tachysystole (more than 5 contractions in 10 minutes with and without fetal heart rate decelerations) or hypertonus (a single contraction lasting more than 2 minutes) during the time the foley is in place. We will also be assessing time to complete dilation and delivery, total time on L&D, rate of cesarean delivery, number of patients able to achieve active labor, and severe maternal morbidity- composite of 21 indicators, such as hysterectomy, eclampsia, sepsis, and blood products transfusion **and b**) **neonatal outcomes:** neonatal cord gases (arterial pH), neonatal Apgar scores at 1 and 5 minutes, and a composite of serious neonatal morbidity up to 7 days of life defined as need for respiratory support within 72 hours after birth, hypoxic-ischemic encephalopathy, seizure, infection, meconium aspiration syndrome, intracranial or subgaleal hemorrhage, hypotension requiring vasopressor support, admission to neonatal intensive care unit.

Secondary Efficacy Endpoint(s): The secondary outcomes are to examine recruitment feasibility, willingness of participants to be randomized to guide recruitment periods for future studies, and to assess medication tolerability through participant experience surveys.

12.2 Sample size determination

We plan to recruit 15 patients per group (30 total) based on the "rule of 12" that is recommended for pilot studies that aim to estimate average values and variability to plan larger studies,²⁴ and to accommodate an estimated 25% intrapartum cesarean rate. Based on 80% power, a two-sided alpha of 0.05, and prior data, we estimate that this sample size would enable us to detect a difference of at least 25 uterine contractions between the two study groups (140-150 on average during labor for patients induced with misoprostol and Cook balloon).

There were approximately 800 inductions among nulliparous patients at LPCH in 2020. We anticipate excluding ~200 patients based on eligibility criteria. Based on previous institutional studies and institutional practices, we expect 50% of patients to be approached for enrollment based on our experience and approximately 50% of patients who are approached to agree to participate in research study. This will result in approximately 150 patients who would agree to participate during one year.

The analysis plan and sample size calculation were developed in consultation with Maternal-Fetal Medicine Senior Biostatistician, [name] (Co-I).

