- 5. Pregnancies complicated by oligohydramnios
- 6. Fetuses with an estimated fetal weight >4500 gm by recent ultrasound or Leopold's exam on admission
- 7. Patients with class 3 obesity (BMI >40)

- 8. Fetuses with a persistent category 2 or 3 fetal heart tracing at labor induction admission
- 9. Vaginal bleeding at the time of randomization
- 10. Any indication for scheduled cesarean delivery
- 11. Hypersensitivity to oxytocin
- 12. Uterine contractions \geq 5 in10 minutes that is sustained for at least 30 minutes
- 13. Hypersensitivity to prostaglandins

Interventions:

- 1. Active group: Mifepristone 200 mg po + Transcervical (Cook) Balloon
- 2. Standard group: Misoprostol 50 mcg po+ Transcervical (Cook) Balloon

Medications:

Mifepristone 200mg po Misoprostol 50 mcg po

Analysis: Intent to Treat

Outcome Measures:

Primary outcomes:

• Generation of preliminary data comparing obstetric and neonatal outcomes among patients randomized to misoprostol 50 mcg versus mifepristone 200 mg

Obstetric outcomes:

- Number of uterine contractions with and without fetal heart rate decelerations during the time the foley is in place
- Rate of uterine tachysystole (≥ 5 contractions in 10 minutes that is sustained for at least 30 minutes) or hypertonus (a single contraction lasting more than 2 minutes) during labor
- Time to delivery
- Time to complete cervical dilation
- Total time on the Labor and Delivery unit
- Rate of cesarean delivery (CD)
- Rate of failed induction of labor per ACOG guidelines
- Composite of serious maternal morbidity based on CDC severe maternal morbidity and mortality (including acute myocardial infarction, aneurysm, acute renal failure, adult respiratory distress syndrome, amniotic fluid embolism, cardiac arrest/ventricular fibrillation, conversion of cardiac rhythm, disseminated intravascular coagulation, eclampsia, heart failure/arrest during surgery or procedure, puerperal cerebrovascular disorders, pulmonary edema/acute heart failure, severe anesthesia complications, sepsis, shock, sickle cell disease with crisis, air and thrombotic embolism, blood products transfusion, hysterectomy, temporary tracheostomy, ventilation)

• Neonatal outcomes:

- Comparison of neonatal cord gases (arterial pH) and neonatal APGAR scores at 1 and 5 minutes

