4.3 End of Study Definition

The study will be complete once enrollment has been completed. The goal is 30 patients with 15 in each arm.

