4.4 Sample Size

We plan to recruit 15 patients per group (30 total) based on the "rule of 12" that is recommended for pilot studies that aim to estimate average values and variability to plan larger studies,²⁴ and to accommodate an estimated 25% intrapartum cesarean rate. Based on 80% power, a two-sided alpha of 0.05, and prior data, we estimate that this sample size would enable us to detect a difference of at least 25 uterine contractions between the two study groups (140-150 on average during labor for patients induced with misoprostol and Cook balloon). The analysis plan and sample size calculation were developed in consultation with Maternal-Fetal Medicine Senior Biostatistician, [name] (Co-I).

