6. RANDOMIZATION

Randomization will occur at the time of labor induction admission.

Randomization may occur upon confirmation that all exclusion/inclusion criteria are satisfied, after verification of participant consent and HIPAA authorization, and a transcervical balloon is placed by the OB provider. Of particular importance, careful consideration will be given to the patient's history and fetal status to determine final eligibility. Study staff will also verify participant contact information and obtain a Release of Information.

The MFM Research team will review the following before randomization:

- Complete review of all exclusion and inclusion criteria
- Informed consent obtained
- Fetal status and cervical exam to confirm eligibility
- Verification by OB provider that transcervical balloon is in place

Pharmacy randomization:

- The LPCH pharmacy will randomize the study medication and dispense to the Labor and Delivery medication dispense system, Pyxis.
- The L&D nurse caring for the participant will provide the medication and instructions

The LPCH pharmacy will attain records of randomization.

Both groups, will undergo continuous external fetal monitoring and tocometry throughout the entirety of labor induction per standard of care.

[figure not shown]
The categories of patients randomized:

Patients consenting to the study will be randomized in 1:1 blocks to two treatment groups

Group 1: Patients randomized to the mifepristone group will receive mifepristone 200 mg po treatment.

Group 2: Patients randomized to the misoprostol group will receive misoprostol 50 mcg po treatment.

Study Design

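### For outcomes that a cesarean leaves unobserved, 15 per group does not keep 12 per group after the plan's own 25% allowance (minor; wording fix, N unchanged)

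*Combined protocol and SAP*

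**What the plan says.** Section 4.3 sets the target: "The goal is 30 patients with 15 in each arm". Sections 4.4 and 12.2 give the same justification for it. The size is "based on the 'rule of 12' that is recommended for pilot studies that aim to estimate average values and variability to plan larger studies", and it is also meant "to accommodate an estimated 25% intrapartum cesarean rate". The next sentence adds a power argument: "Based on 80% power, a two-sided alpha of 0.05, and prior data", the size is said to suffice to "detect a difference of at least 25 uterine contractions between the two study groups". No standard deviation is given.

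The plan does not show how 15 was obtained. It does not say that the 12 is per group or that it must remain after cesareans, and it does not name any outcome that a cesarean would remove. The synopsis states "Analysis: Intent to Treat".

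Three other places bear on the point:

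- Section 6.2 calls time to complete cervical dilation the primary outcome.
- Section 12.3 compares continuous variables with the Mann-Whitney U test and gives no censoring or ranking rule for a value that is never observed.
- The synopsis and section 3.1 count contractions while the balloon is in place, and list the cesarean rate and neonatal outcomes among the primary outcomes.

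**The concern.** Accommodating a rate when setting a sample size ordinarily means enrolling extra women because some will not contribute to an estimate. Read that way, the sentence implies that 12 per group survive a 25% loss, and 15 per group does not achieve this.

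The rule of 12 is the only part of the justification that a reader can check, since the power statement lacks a standard deviation. The pilot exists to estimate averages and variability for planning larger studies. A reader should therefore be able to tell how many women per group stand behind each estimate. At present the text suggests at least 12 for every outcome, and by its own inputs that does not follow for an outcome that a cesarean cuts off.

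**Working it through.** **Inputs**

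- Planned size: 15 per group, 30 in total (sections 4.3, 4.4, 12.2), allocated 1:1 (section 6).
- Pilot target: 12. The plan gives only the name of the rule. Reading it as 12 per group is an inference from the sentence, which speaks of patients per group.
- Allowance: 25% (sections 4.4, 12.2). Treating it as a loss is an assumption, and is made only for an outcome that a cesarean leaves unobserved.

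**1. The plan's figure.** 12 x (1 + 0.25) = 15, an exact match to the stated size. The plan does not show this step, so it is a plausible origin and no more; 15 could also be a rounded choice.

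**2. Size needed to keep 12 after a 25% loss.** 12 / (1 - 0.25) = 16 per group, 32 in total. Check: 16 x 0.75 = 12.

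**3. What 15 leaves.** 15 x 0.75 = 11.25 per group, 22.5 in total. The shortfall is 12 - 11.25 = 0.75 of a woman per group.

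**4. Largest loss that 15 can absorb.** 1 - 12/15 = 0.20, that is 20%.

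**5. Effect on precision.** The standard error of a mean scales with 1/sqrt(n), so the ratio is sqrt(12/11.25) = 1.033, about 3% wider than with 12.

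**6. Which outcomes are affected.**

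- *Time to complete dilation:* unobserved if the cesarean comes before full dilation. If a fraction f of cesareans follows full dilation, the loss is 0.25 x (1 - f) and 15 x [1 - 0.25 x (1 - f)] remain. The documents do not give f. With f = 0, 11.25 remain; with f = 0.2, the loss is 20% and exactly 12 remain; with f = 1, all 15 remain. So 11.25 is the worst case.
- *Contractions while the balloon is in place:* section 6.2 describes the move to cesarean as part of management after the balloon is out, so this count would normally be complete by then. All 15 stay. (Sections 12.1 and 12.2 also refer to contractions in or during labor; that inconsistency is a separate point.)
- *Cesarean rate, total time on the unit, cord pH, Apgar scores and the morbidity composites:* all observable after a cesarean. All 15 stay.

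**The case against.** The strongest reply is that nothing in the plan says women with a cesarean leave an analysis. The analysis is by intent to treat, cesarean is itself an outcome, and most listed outcomes are observed whatever the mode of delivery. On that view 15 per group exceeds 12 and there is no shortfall. This stands for every outcome that all women have, and it limits the point accordingly. It does not rescue the sentence: if no outcome is lost, a 25% cesarean rate needs no accommodating, and the text does not say what the allowance is for.

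A second reply is that the same paragraph also rests on 80% power for a difference of 25 contractions, so the rule of 12 is not the sole support. That is true. But the power claim cannot be verified without a standard deviation, and it does not make the rule-of-12 statement correct.

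A third reply is size: under one woman per group, in a pilot. That also stands, and it is why the point is minor.

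A reader might quote binomial chances as a sign of something worse. If every woman had a 25% chance of being lost, at least 12 would remain in one group of 15 with probability 0.46, and in both groups with probability 0.46 x 0.46 = 0.21. Those figures assume that every cesarean is unevaluable. Even 16 per group gives only 0.63 for one group and about 0.40 for both, so they do not single out 15 as a failure.

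**Conclusion.** The point holds as a minor error in the stated justification. For outcomes that a cesarean makes unobservable, 15 per group with a 25% loss leaves 11.25, below the cited 12, and the rule is met only up to a 20% loss. The shortfall is at most about 0.75 of a woman per group. This rests on reading the rule as 12 per group and on treating the whole 25% as lost for the affected outcome, chiefly time to complete dilation when the cesarean precedes full dilation.

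Two stronger conclusions are tempting, and the documents support neither. One is that only about 11 women per group remain in the trial's analysis: intent to treat, and outcomes that do not depend on mode of delivery, keep all 15. The other is that the plan demonstrably inflated 12 by the wrong formula: 15 equals 12 x 1.25, but no derivation is shown. Nor does the gap amount to a material sample-size error that calls for a larger trial.

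**What to change.** Keep N at 30 and amend the justification in sections 4.4 and 12.2, in the same words in both places. Suggested text:

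*With 15 women per group, about 11 per group would remain for outcomes made unobservable by an intrapartum cesarean (chiefly time to complete cervical dilation, when the cesarean precedes full dilation) if 25% are lost. For those outcomes the rule of 12 per group is met only up to a 20% loss. All 15 women per group are analysed by intent to treat for every other outcome.*

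The cost is a few sentences of protocol wording and a stated figure that is slightly less favourable than the present text implies. No additional participants are needed, and neither the tests nor the allocation change.

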12.3 Analyses

We will compare the number of uterine contractions and other continuous variables using Mann-Whitney U test and will use Fisher's exact test for categorical variables. Differences will be considered statistically significant using two-sided tests (P<0.05).

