Mifepristone as an Adjunct to Transcervical Balloon for Labor Induction (MiLI): A Randomized Clinical Trial National Clinical Trial (NCT) Identified Number: 05097326 Principal Investigators: [name], MD and [name], MD MS Research Coordinator: [name], Medicine

May 11, 2022

Mifepristone as an Adjunct to Transcervical Balloon for Labor Induction: A Randomized Clinical Trial (MiLI)

Objective: Our goal is to generate preliminary data on perinatal outcomes, establish recruitment feasibility, and medication tolerability among patients who receive mifepristone for labor induction for live birth. Our aims are to 1) generate preliminary data on the impact of mifepristone use on obstetric and neonatal outcomes and 2) examine recruitment feasibility and willingness of participants to be randomized to guide recruitment periods for future studies

Organization: Stanford University School of Medicine, Department of Obstetrics and Gynecology

Clinical Center: Stanford/LPCH OB clinic and Labor & Delivery

Design Type: Parallel group, two-arm, non-blinded, randomized control trial

Inclusion Criteria:

- 1. Pregnant patients between ages 18 to 45 years
- 2. Singleton, live gestation
- 3. Nulliparous
- 4. Gestational age between 37 weeks 0 days 42 weeks 0 days
- 5. Fetus in cephalic presentation
- 6. Patients admitted for labor induction
- 7. Patients who are not in labor with intact membranes

8 Patients with no contraindication for vaginal delivery (placenta previa, vasa previa, active genital herpes)

9. Patients with no contraindications for mifepristone (chronic adrenal failure, concurrent longterm corticosteroid therapy, history of allergy to mifepristone, or other prostaglandins, hemorrhagic disorders or concurrent anticoagulant therapy, inherited porphyria, or an intrauterine device (IUD) in place)

10. Patients with a Bishop score <6 at time of randomization

11. Transcervical balloon in place <3 hours prior to the time of randomization without prior cervical preparation

*For patients who meet the above inclusion criteria 1-10 and who those who decline randomization will be offered enrollment for chart review only.

Exclusion Criteria:

1. Significant cardiac, renal, or hepatic maternal comorbidities, severe gestational hypertension or preeclampsia with severe features

- 2. Pregnancies complicated by major fetal anomalies
- 3. Patients with a uterine scar
- 4. Pregnancies complicated by fetal growth restriction (Estimated fetal weight <10%)

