6.2 Induction of Labor: Study Groups

At LPCH cervical preparation typically begins with prostaglandins (misoprostol and dinoprostone), 12-hours of transcervical (Cook) balloon placement, or misoprostol and Cook balloon used concurrently. For the purposes of our study, all patients will receive the standard of care for labor induction at LPCH, starting with mechanical induction of labor with the transcervical (Cook) balloon. The Cook balloon will remain in place for a maximum of 12 hours. After 12 hours of Cook balloon placement, the OB provider will deflate the Cook balloon and perform a cervical exam. If the balloon spontaneously expels prior to 12 hours, the time will be noted and a cervical exam performed. The balloon will be removed at any point in the setting of spontaneous rupture of membranes (SROM) per standard of care, to minimize risk of intraamniotic infection. After a balloon expulsion, balloon removal in the setting of SROM or after 12 hours of balloon placement and removal, the provider will manage the labor induction based on standard of care practice, including using up-titration of oxytocin, amniotomy when deemed safe and appropriate, and transitioning to cesarean or operative birth if deemed necessary by the provider. Patients who receive misoprostol will be eligible to receive additional doses of misoprostol 50 - 100 mcg, because of its known safety. Patients who receive mifepristone will not be eligible for additional doses of misoprostol because based on the pharmacokinetics of mifepristone, the ripened cervix could potentiate uterine tachysystole.

Once the patient achieves complete cervical dilation, time spent in the second stage of labor will be at the discretion of the OB provider given variability among patients and providers.

As the standard of care, oxytocin is indicated when a modified Bishop score of 8 or greater is observed or if spontaneous rupture of membranes occurs during the ripening process. Intravenous oxytocin will begin at 1 milliunits per minute about 12 hours after mifepristone dispense and will be titrated per LPCH protocol. Amniotomy will performed at the discretion of the provider.

Maternal pulse and blood pressure will be recorded during the ripening process to assess for the incidence of maternal blood pressure or maternal heart rate changes; mean arterial pressures and

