pulse measurements will be recorded every 15 minutes for the first hour of the induction process and then hourly during the first 4 hours of the induction process. If 2 vital sign abnormalities are noted during this period, the OB provider will be notified, and the standard of care work up will be initiated. (See section 2.3.2) Abnormal vital signs include Heart rate > 110 beats per minute or <50 beats per minute, systolic blood pressure (mm Hg) > 160 or < 45 or diastolic blood pressure > 110 or < 85 or MAP <65 mm Hg. Patients will assessed for the presence of known potential side effects from mifepristone or misoprostol by patient interview on postpartum day one. All patients will undergo continuous electronic fetal heart rate monitoring and tocometry until the time of delivery.

Cervical exams will be performed per standard of care by OB providers and recorded. The primary outcome is time to complete cervical dilation. Once the patient achieves complete cervical dilation, time spent in the second stage of labor will be at the discretion of the provider.

Placentas will be sent out to Pathology after delivery if deemed indicated for both groups by the provider. Both groups will have their placentas analyzed if there are clinical indications for the test.

Time and mode of delivery will be recorded into the REDCap database.

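### Section 12.3 gives no value or rank for time to complete dilation to participants delivered by cesarean before full dilation, so the comparison would cover only a post-randomization subset

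*Combined protocol and SAP*

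**What the plan says.** Section 12.3 is the whole analysis plan: Mann-Whitney for continuous variables, Fisher's exact test for categorical ones, two-sided at 0.05. Its sentence on continuous outcomes is "We will compare the number of uterine contractions and other continuous variables using Mann-Whitney U test". The synopsis gives the analysis principle in one line: "Analysis: Intent to Treat".

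The standing of time to complete dilation varies. The synopsis and section 3.1 list it among several primary obstetric outcomes. Section 6.2 says "The primary outcome is time to complete cervical dilation". Section 12.1 introduces it with "We will also be assessing time to complete dilation and delivery". The power statement in 12.2 concerns uterine contractions.

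Cesarean after randomization is foreseen. Once the balloon is out, section 6.2 allows "transitioning to cesarean or operative birth if deemed necessary by the provider". Section 12.2 sets the sample size partly "to accommodate an estimated 25% intrapartum cesarean rate", and describes the design as suited to "pilot studies that aim to estimate average values and variability to plan larger studies".

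No section defines when the clock for time to complete dilation starts. The inclusion criteria read "Transcervical balloon in place <3 hours prior to the time of randomization without prior cervical preparation", so balloon placement and randomization can be up to 3 hours apart.

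**The concern.** A Mann-Whitney test needs a value, or at least a rank, for everyone it compares. A participant sectioned at 6 cm, say, has no time to complete dilation. With no rule, the software treats that time as missing and the test runs on those who reached full dilation. That group is formed by an event after randomization which may depend on both labor speed and arm, so the two arms are no longer compared as randomized.

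For a pilot, the averages and spread matter as much as the P value. If slow labors are the ones that end in cesarean, the remaining times look shorter and less variable than those of the whole randomized group, and a larger trial planned on them alone inherits that.

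**Working it through.** **The plan's own figure.** Rule of 12 enlarged for 25% cesareans: 12 × 1.25 = 15 per arm, the stated number (12 / 0.75 would give 16). This suggests the authors expected some cesarean participants not to contribute, but the text does not say so. A larger sample replaces lost numbers; it does not restore the randomized comparison.

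**How many have no time.** From 12.2: n = 30, cesarean 25%.
- Upper end, every cesarean before full dilation: 30 × 0.25 = 7.5 without a time, leaving 22.5. Chance of at least one: 1 − 0.75^30 = 99.98%.
- Half of cesareans before full dilation (assumed): 30 × 0.125 = 3.75, leaving 26.25. Chance of at least one: 1 − 0.875^30 = 98.2%.

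**What selection could do.** The documents give nothing on this, so every input here is assumed. Log labor time is normal with SD 0.45. A cesarean score has correlation ρ with log time, and the participant is sectioned if the score exceeds a cut-off c. ρ = 0 means cesarean is unrelated to speed; ρ = 1 means exactly the slowest are removed.

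*Planning values.* With 25% sectioned, c = 0.6745 and r = φ(c)/0.75 = 0.4237. Completers' log-time variance as a share of the full variance is 1 − ρ²(c·r + r²).

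| Sectioned before full dilation | ρ | Variance ratio | Median too low by |
|---|---|---|---|
| 25% | 0 | 1.00 | 0% |
| 25% | 0.5 | 0.88 | 9% |
| 25% | 1 | 0.53 | 13% |
| 12.5% | 0 | 1.00 | 0% |
| 12.5% | 0.5 | 0.92 | 5% |
| 12.5% | 1 | 0.67 | 7% |

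The yardstick is a latent time, the one each participant would have had without cesarean.

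*Arm comparison.* Equal labor speed in both arms (median 17 h), 15 per arm, 8,000 simulated trials per setting, nominal 5%. Mann-Whitney rejection among completers, with the worst-rank version (cesarean before full dilation ranked last):

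| Sectioned, arm A v B | ρ | Completers only | Worst rank |
|---|---|---|---|
| 25% v 25% | 0 / 0.5 / 1 | 4.7 / 4.6 / 4.3% | 4.5 / 4.9 / 4.7% |
| 20% v 30% | 0.5 / 1 | 4.6 / 6.5% | 6.3 / 5.1% |
| 15% v 35% | 0 / 0.5 / 1 | 4.5 / 5.4 / 14.2% | 15.0 / 10.8 / 5.7% |

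At 15% v 35% the completers' medians differ falsely by 0 / 1.0 / 1.8 h, and the arm with more cesareans looks faster. If only half of those cesareans precede full dilation (7.5% v 17.5%), completers-only rejection is about 5% at ρ = 0.5 and 7% at ρ = 1.

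*Model dependence.* A second assumed model (median 18 h, log-SD 0.4, 4,000 trials) draws the number sectioned in each arm and then removes participants by their rank within the arm. At 15% v 35% it rejects in 4.4% with no link, 10.5% with a score that is half rank and half noise, and 20.1% with a complete link. At 25% v 25% with a complete link it rejects in 14.1%. It makes cesarean depend on how a labor ranks against others in the same arm, which is artificial, but it shows that the size is not settled by any one model.

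*Power.* Medians 14 v 20 h (assumed), 25% sectioned in both arms, ρ = 0: completers only 39%, worst rank 19%.

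**The case against.** The strongest reply is that the plan excludes nobody. A reader might infer that cesarean participants are to be dropped in breach of intent to treat. The documents do not say that: the synopsis names the principle without defining it, and 12.3 is silent. This stands. What is shown is an undefined value and the subset that follows by default.

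A reader might also take the larger figures above as the likely harm. They stack assumptions: the slowest labors are exactly those removed, all cesareans precede full dilation and, for 14.2%, the arms split 15% v 35%. With balanced cesarean rates the main model shows no inflation. The variance and median shortfalls are measured against a latent time that a competing-event analysis does not estimate, so they warn against planning on completers alone; they are not the price of omitting the fix. This also stands.

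Third, part of the picture is already planned. Cesarean rate and failed induction are listed outcomes, and time to delivery and total time on the unit remain defined after a cesarean. That limits the damage but leaves time to complete dilation without a rule.

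Finally, the only outcome with a power statement is contractions. It would be wrong to infer that the trial's powered comparison is undermined. The conflicting wording on which outcome is primary is a separate matter.

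**Conclusion.** The gap is real and should be fixed. As written, 12.3 can rank time to complete dilation only in participants who reach full dilation, and at the plan's own cesarean rate at least one of 30 will almost certainly lack a value: up to 7.5 expected, or 3.75 if half of cesareans follow full dilation.

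The omission is certain; its effect is not. The documents give neither the size nor the direction of the bias. It is nil if cesarean is unrelated to labor speed. In the main assumed model a clearly raised false-positive rate needs strong selection together with a large imbalance in cesarean; the second model can raise it with strong selection alone. The documents do not support a claim that the trial will produce a false finding. The firmer consequence is that averages and spread for this outcome would describe a selected group while being offered for planning a larger trial.

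**What to change.** In 12.3:

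1. Measure time to complete dilation from randomization, in all randomized participants in their assigned arm.
2. Keep the Mann-Whitney test, with cesarean before full dilation ranked (tied) after every observed time.
3. Show the cumulative incidence of complete dilation by arm, with cesarean before full dilation as a competing event. Censor anyone withdrawn before delivery (section 9.2 allows this) at withdrawal. Such a participant has no rank in step 2, so report how many there are in each arm.
4. Give the cesarean rate by arm beside these results.
5. Label any median or spread among participants who reached full dilation as conditional on that event, and do not plan the larger trial on it alone.

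The cost is a few sentences. Section 6.2 already has cervical exams and time and mode of delivery recorded. The pharmacy keeps the randomization record (section 6), which must carry the time.

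There are two downsides. The ranked result partly reflects cesarean: with equal labor speed and 15% v 35% sectioned it rejects in about 15% of trials at ρ = 0 and 11% at ρ = 0.5, which is why step 4 is needed. Power is also lower than among completers (19% v 39% in the assumed 14 v 20 h case). With 15 per arm the comparison should be read as estimation, not as a test of efficacy.
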